7.2 Sample Size and Power

We calculated power for comparing our primary outcome (overall QOL) in the Primary Objective using a standard approach for linear mixed models. Because we will assess outcomes for patients and partners separately, we applied a Bonferroni-corrected, two-sided alpha of 0.025 to allow for separate overall tests for patients and partners. This is because, although dyadic data will be modeled simultaneously, conclusions may differ for patients and partners. Based on our pilot test of PERC, we assumed a common standard deviation for the overall QOL scores of 15 points and a within-person correlation between repeated measurements of 0.75. Also, we allowed for losing up to 7% of participants every 4 months, for a total attrition of 20% through 12 months.

Under these assumptions (based on our preliminary studies), we report power for two scenarios, first allowing for attenuating effects, and then assuming constant effects. For the first scenario, we assumed that, on average, PERC would result in improved QOL relative to the control condition, but that these benefits might realistically be expected to decrease somewhat over time. Assuming that the mean difference between groups would be 7.5 points in overall QOL scores at 4 months (i.e., a moderate effect size of 0.5 that would represent a clinically meaningful difference immediately following the intervention) and that this would decrease by 15% every 4 months, randomizing 125 dyads per group would provide 90% power to reject the overall null hypothesis of no differences between groups across all time points. Furthermore, with this scenario, this sample size would provide 94% power for the 4-month comparison, 83% power for the 8-month comparison, and 51% power for the 12-month comparison. For the second scenario, we assumed that the intervention has a constant effect of 6.5 points at each time point (an effect size of 0.43). This sample size will provide at least 80% power for each comparison.

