7.3 Data Analysis Plans

A detailed analysis plan will be developed prior to initiating the study; the following is a summary of the proposed plan. Unless otherwise specified, all analyses will include all randomized participants, in the arm to which they are randomized, regardless of the extent of intervention received (intention-to-treat).

Primary Objective: We will compare the longitudinal mean change in overall QOL between groups using analysis of covariance (ANCOVA), conducted using linear mixed models. Data for patients and partners will be fit together in the same model (accounting for within-dyad correlation), which will allow us to readily assess for differential treatment effects between patients and partners. Mixed models will allow for the inclusion of all observed data for all dyads, assuming any missing data are

missing at random. Each model will include fixed effects (separate for patient or partner) for group, month, group-by-month interactions, the baseline value of the outcome scale, baseline treatment type (surgery and radiation +/-hormonal therapy), number of baseline comorbidities, baseline couple relationship quality, baseline family disruptions, age, race/ethnicity, education, income, and number of people supported by the income. These covariates were selected because they are potentially associated with QOL. Models will include random dyad and participant nested within dyad effects to account for within-dyad and within-person correlations between longitudinal responses. For the primary comparison, separately for each participant type, we will first test for any differences between groups across all 3 time points using an appropriately specified 3 degree of freedom linear contrast. Only if this test is significant ($p \leq 0.025$), will we test for group differences at each time point.

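### The time-point powers in section 7.2 leave out the overall-test gate and the baseline covariate that section 7.3 plans, so they are not the powers of the planned procedure

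*Combined protocol and SAP*

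**What the plan says.** **Section 7.2 (power).** The assumptions are an SD of 15 for the overall QOL score, a "within-person correlation between repeated measurements of 0.75", and loss of up to 7% of participants every 4 months. Two-sided alpha is 0.025, set "to allow for separate overall tests for patients and partners".

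- Scenario 1 has a 7.5-point difference at 4 months that shrinks by 15% every 4 months. For it, "randomizing 125 dyads per group would provide 90% power to reject the overall null hypothesis", and "this sample size would provide 94% power for the 4-month comparison", with 83% at 8 months and 51% at 12 months.
- Scenario 2 has a constant 6.5-point difference: "This sample size will provide at least 80% power for each comparison".

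**Section 7.3 (analysis).** Longitudinal change in QOL is compared "using analysis of covariance (ANCOVA), conducted using linear mixed models". The fixed effects include "the baseline value of the outcome scale". For each participant type a 3-df test across the three visits comes first. Only if it gives p ≤ 0.025 "will we test for group differences at each time point". No level is printed for those follow-up tests. The section describes itself as a summary of a fuller plan still to be written.

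**The concern.** Hypothesis 1 (section 2.1) claims benefit at 4, 8 and 12 months, so the time-point tests carry the claim that the effect lasts. A reader of section 7.2 will take the printed powers as the chance that each visit is declared positive under section 7.3.

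One pair of figures shows that this cannot be so. A 4-month comparison that is run only after the overall test succeeds cannot succeed more often than that test, yet 94% stands beside 90%. A second difference works the other way. Section 7.2 equates 7.5 points with an effect size of 0.5, that is 7.5/15, so 15 is the SD of the raw score and not a residual SD after adjustment for baseline. The planned ANCOVA would use the smaller residual SD.

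If only the gate is added, the printed figures are too high. If baseline adjustment at 0.75 is added as well, they are too low.

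**Working it through.** **Inputs (section 7.2).** SD 15; correlation 0.75, taken as equal between all pairs of visits; 125 per group; retention 0.93, 0.93² = 0.865 and 0.93³ = 0.804, with dropout taken as monotone; two-sided 0.025, so z = 2.241. Scenario 1 differences: 7.5, 7.5 × 0.85 = 6.375, 6.375 × 0.85 = 5.42. Scenario 2: 6.5 at each visit. Power is computed for one participant type.

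**Step 1. Reproduce the printed figures with no gate and no covariate.** The standard error at 4 months is 15 × √(2/(125 × 0.93)) = 1.967. At 8 and 12 months the mixed model borrows from earlier visits, giving 2.000 and 2.027. Power = Φ(difference/SE − 2.241).

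- Scenario 1, 4 months: 7.5/1.967 − 2.241 = 1.57, power 94.2% (printed 94%).
- Scenario 1, 8 months: 6.375/2.000 − 2.241 = 0.95, power 82.8% (printed 83%).
- Scenario 1, 12 months: 5.42/2.027 − 2.241 = 0.43, power 66.7% (printed 51%).
- Scenario 2: 85.6%, 84.4% and 83.3% (printed: at least 80%).

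The 12-month figure does not reproduce. Neither does the overall 90%, which comes out at 86.7% (step 3). That is a separate issue.

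**Step 2. Is another reading possible?** At 4 and 8 months, unadjusted, a level of 0.05 gives 96.8% and 89.0%, and 0.0125 gives 90.6% and 75.5%. At 0.025 with baseline adjustment at 0.75, the powers are 99.98% and 99.4%. A baseline correlation of 0.1 still rounds to the printed pair (94.4%, 83.2%); 0.2 does not (95.0%, 84.4%). So 94% and 83% belong to an ungated test at 0.025 with little or no baseline adjustment.

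**Step 3. Add the gate.** The 3-df test at 0.025 has critical value 9.348. With noncentrality δ′V⁻¹δ, where δ holds the three differences and V is the covariance matrix of their estimates, its unadjusted power is 86.7% in scenario 1 and 80.0% in scenario 2. The 4-month comparison therefore cannot reach 94% on the recomputed gate either.

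**Step 4. Add the baseline covariate.** With baseline-to-follow-up correlation r, the residual SD is 15 × √(1 − r²). At r = 0.75 this is 9.92, and the standard errors fall to 1.301, 1.341 and 1.378.

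The chance of passing the gate and then the time-point test at 0.025, from 1,000,000 simulated sets of three estimates, is:

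| Baseline correlation | Scenario 1, 4/8/12 months | Scenario 2, 4/8/12 months |
|---|---|---|
| none (unadjusted) | 86.1 / 78.5 / 64.5% | 76.7 / 76.0 / 75.3% |
| 0.29 | 89.6 / 82.8 / 69.0% | 81.7 / 80.9 / 80.2% |
| 0.5 | 95.6 / 90.8 / 78.7% | 91.0 / 90.3 / 89.6% |
| 0.75 | 99.96 / 99.4 / 95.4% | 99.7 / 99.5 / 99.3% |

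Scenario 2 keeps at least 80% at every visit through the gate once the baseline correlation is about 0.29 or more.

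**The case against.** The strongest reply is that section 7.2 never calls its time-point powers joint probabilities. It gives the overall power and then a power for each comparison, and ungated powers are a common way to report. On that reading 94% beside 90% is a labelling gap, and the two figures even bound the gated 4-month power between 0.94 + 0.90 − 1 = 84% and 90%. This stands in part, and it is why relabelling is an acceptable remedy. But the figures carry no label, and the bound uses an overall power that does not itself reproduce.

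A second reply is that powering on the unadjusted SD and then analysing by ANCOVA is conservative. That is correct, and it limits the point.

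A third is that the baseline correlation is not really missing. Section 7.2 gives 0.75 between repeated measurements, and the table in section 5.1 lists FACT-G at baseline and at every follow-up. The natural reading is that 0.75 covers baseline too, although section 7.2 does not say so separately. It would be too strong to say that the plan gives no such figure, or that the 80% claim is false for the planned analysis.

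A reader might also infer from the missing level that the follow-up tests have no control of multiplicity. The documents do not support that. The gate is itself such a rule, 0.025 can be recovered from section 7.2, and section 7.3 is only a summary. Stricter rules across visits are optional and cost power.

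**Conclusion.** The point holds as a mismatch between sections 7.2 and 7.3. The printed 94%, 83% and at least 80% are powers of an ungated, unadjusted comparison at 0.025, not of the planned gated ANCOVA. In scenario 2 the planned gate alone lowers them to 77/76/75%. The gate with baseline adjustment at 0.75 raises them to 99.7/99.5/99.3%.

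A reader might infer that the trial is underpowered, and the documents do not show this. Falling below 80% in scenario 2 through the gate needs a baseline correlation under about 0.29 alongside 0.75 between visits, and nothing in the plan suggests that. At 0.75 the net effect is that section 7.2 understates power. Sections 1.1, 2.0 and 4.3 also plan 400 dyads; at 200 per group, gated scenario 2 is 95/95/94% even unadjusted.

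Nor should a reader infer that all the other figures in section 7.2 are sound. From the stated 15% decay, the 12-month 51% comes out at about 67% and the overall 90% at about 87%.

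The results assume equal correlation between visits, monotone 7% dropout, 15 as the raw-score SD, and follow-up tests at 0.025. The gate argument does not depend on the baseline correlation.

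**What to change.** In section 7.2, recompute and restate the overall and time-point powers for the planned procedure: the 3-df gate, then each visit at 0.025, under ANCOVA with baseline QOL. State the assumed correlation between baseline and follow-up. If the present figures are kept, label them as marginal (without the gate) and unadjusted, and print the gated values beside them.

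As a minor clarification, name 0.025 in section 7.3 as the level of the follow-up tests.

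The cost is a few sentences and a short recalculation. No new data and no change of design are needed.

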2.0 STUDY OBJECTIVES/AIMS AND ENDPOINTS

In this randomized controlled trial, we will examine the efficacy of a couple-focused, web-based tailored prostate cancer symptom management program (PERC). We will use a two-group (**PERC versus NCI website**) randomized controlled design and collect data at baseline (T1) and 4 (T2), 8 (T3), and 12 months (T4) among 800 patients (400 patient - partner dyads) completing initial treatment for localized prostate cancer and their intimate partners.

2.1 Primary Objective: Assess the efficacy of PERC for improving QOL (total score and subscale scores of the physical, social, mental, and functional domains) among patients and their intimate partners.

H 1: Patients and their intimate partners randomized to PERC will report a larger increase in QOL scores (as assessed by the Functional Assessment of Cancer Treatment, FACT-G) than those randomized to the control group (usual care plus the National Cancer Institute prostate cancer website, the NCI website) at 4, 8, and 12 months post-baseline

2.1.1 Our primary outcome is the total QOL score, and each of the QOL subdomains are secondary outcomes.

2.2 Secondary Objectives: Test the effects of PERC on symptom appraisals and coping resources.

H 2: Patients and their intimate partners randomized to PERC will report greater improvement in secondary outcomes, positive appraisals of illness and coping resources, i.e., self-efficacy in symptom management, greater social support, and use of more healthy behaviors, at follow-ups than those randomized to the control group.

2.3 Exploratory Objective: Explore whether patients' race/ethnicity, education, type of cancer treatment, and couples' relationship quality at baseline moderate the effects of PERC on patient and partner QOL at follow-ups.

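### No level or adjustment is stated for the three time-point tests after the 3-df gate; if the effect is confined to one visit, a false time-point claim can reach about 4.2–4.8% per role

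*Combined protocol and SAP*

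**What the plan says.** Section 7.2 divides alpha between the two roles: "we applied a Bonferroni-corrected, two-sided alpha of 0.025 to allow for separate overall tests for patients and partners". Section 7.3 says that, separately for each role, the analysis will first "test for any differences between groups across all 3 time points using an appropriately specified 3 degree of freedom linear contrast", with p ≤ 0.025 as the criterion. Only after that, it says, "will we test for group differences at each time point". No significance level, ordering or adjustment is given for these follow-on tests. The section describes itself as a summary, with a detailed analysis plan to follow.

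H1 in section 2.1 states the expected benefit "at 4, 8, and 12 months post-baseline". On the course of the effect, section 7.2 says that "these benefits might realistically be expected to decrease somewhat over time", and it works this out as a 15% fall every 4 months.

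**The concern.** An overall test followed by separate tests controls the false-claim rate when all the separate nulls are true. With three nulls it does not control the rate when only some are true. If PERC works at one visit, that effect opens the gate almost every time. The other two visits are then each tested with nothing protecting the pair, because no step tests whether both are null.

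What is at stake is the claim about duration. The three surveys are meant to show short, intermediate and long-term effects (section 7.1). If the effect were present at 4 months and gone by 8, the time-point tests would be the basis for saying that it lasted. That is the situation in which the procedure as written protects least.

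**Working it through.** **Inputs.** All are from section 7.2 unless noted. SD: "we assumed a common standard deviation for the overall QOL scores of 15 points". Correlation: "within-person correlation between repeated measurements of 0.75". 125 dyads per group. Loss of 7% per 4 months, leaving 125 × 0.93 = 116.3, 125 × 0.93² = 108.1 and 125 × 0.93³ = 100.5 per group. Effect 7.5 points at 4 months, then 7.5 × 0.85 = 6.375 and 7.5 × 0.85² = 5.42; or a constant 6.5. Section 7.3 specifies ANCOVA. If baseline also correlates 0.75 with each visit (an assumption), the adjusted correlation between visits is (0.75 − 0.75²)/(1 − 0.75²) = 0.1875/0.4375 = 0.43.

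**Step 1: the level implied for each time-point test.** The mixed-model standard errors without baseline adjustment are 1.967, 2.000 and 2.027. Power is Φ(effect/SE − z), with z = 2.241 for two-sided 0.025.
- 4 months: 7.5/1.967 − 2.241 = 1.57, giving 94.2% (stated 94%).
- 8 months: 6.375/2.000 − 2.241 = 0.95, giving 82.8% (stated 83%).

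At 0.05 the two powers would be 96.8% and 89.0%; at 0.0125, 90.6% and 75.5%. Only 0.025 matches. The constant scenario agrees: at 0.025 the powers are 85.6/84.4/83.3%, consistent with the stated minimum of 80%, whereas at 0.0125 they are 79.0/77.4/76.1%.

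The stated 51% at 12 months does not follow from an effect of 5.42, which gives 66.7%. It does follow from 7.5 × 0.85³ = 4.61, which gives 51.2%. This does not affect the present point.

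**Step 2: two null visits after the gate is open.** The chance of at least one false claim is 1 − P(|Z₁| ≤ 2.241 and |Z₂| ≤ 2.241). If the two estimates were independent, this would be 1 − 0.975² = 4.9%. At the correlations of the actual estimates it is about 4.2% (about 0.73, no baseline adjustment) and about 4.75% (about 0.41, baseline-adjusted).

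**Step 3: simulation of the whole procedure**, with the gate at 0.025 and then each visit at 0.025. The table gives the chance of any false time-point claim, per role.

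| True effect at T2, T3, T4 | No baseline adjustment | Baseline-adjusted |
|---|---|---|
| 0, 0, 0 | 1.6% | 2.0% |
| 7.5, 0, 0 | 4.2% | 4.8% |
| 7.5, 6.375, 0 | 2.5% | 2.5% |
| Either planned scenario | 0 (no null visit) | 0 (no null visit) |

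With 7.5 points at 4 months only, the gate is passed in more than 99.9% of runs. The excess over 2.5% therefore arises when exactly one visit has a real effect: 4.2/2.5 = 1.7 times to 4.75/2.5 = 1.9 times. If the unstated level were 0.05 instead, the same case would give 8.1–9.3%.

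**Step 4: the two remedies.** With the ordered p-values held to 0.0125, 0.0125 and 0.025 after the gate, the highest simulated rate is about 2.2% without baseline adjustment and 2.4–2.5% with it. The fixed order T2, T3, T4 at 0.025 also holds the rate at about 2.5% or less.

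**The case against.** The strongest reply is that no stated guarantee is broken. Section 7.2 attaches 0.025 to the overall tests of patients and partners, and section 7.3 makes the 3-df contrast the first test of the primary comparison, with the time points as gated follow-up. Nowhere does the plan promise 2.5% across time points within a role. This stands: 2.5% is a benchmark borrowed from the overall test. It is a reasonable one, because H1 names each of the three times.

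A reader might infer that a false time-point claim is generally almost twice as likely as intended. The documents do not support that. The rate is below 2.5% with no effect anywhere, is 2.5% with one null visit, and the question does not arise in either planned scenario.

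A reader might also infer that the sponsor expects the effect to vanish after 4 months. Section 7.2 expects a modest decline that leaves 5.42 points at 12 months. An effect at one visit only is a possibility to guard against, not the planned case.

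Doubling up over both roles is a further temptation: 1 − (1 − 0.042)² = 8.2% or more. That requires each role to have an effect at exactly one visit and the roles to be independent. The model in section 7.3 allows for within-dyad correlation, and no value for it is given.

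Finally, the detail is deferred to a later analysis plan. So the absence of an adjustment is an absence from this summary, and the 0.025 per test is inferred. The inference is firm for the power calculation; the later plan could still set another rule, but nothing in section 7.3 commits it to one.

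**Conclusion.** The point holds as a conditional result. With the implied 0.025 per test, the gate leaves a false-claim rate of up to about 4.2% (no baseline adjustment) to 4.8% (baseline-adjusted) per role when the effect is confined to one visit. In the other patterns examined it is at or below about 2.5%. Because section 7.3 specifies ANCOVA, the upper figure is the more relevant.

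The result rests on the section 7.2 SD, correlation and attrition, on equal correlation across all visits including baseline, and on a normal approximation. Once the gate is passed, the rate depends on the correlation between the time-point estimates and not on the sample size. The difference between the 250 dyads of section 7.1 and the 400 dyads of sections 1.1, 2.0 and 4.3 therefore does not alter it.

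The overall test for each role is unaffected. This is a low-cost improvement that should be made; it does not undermine the primary comparison.

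**What to change.** State in section 7.3 or the detailed analysis plan, before any unblinded analysis, the level of the time-point tests and one of these rules, applied to each role that passes the 3-df gate:

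1. **Fixed order.** Test T2, then T3, then T4, each at 0.025, stopping at the first failure.
2. **Step-down.** Order the three p-values; require the smallest and the second smallest to be ≤ 0.0125 and the largest ≤ 0.025, stopping at the first failure. This is a closed test: the gate covers the three-way null, Bonferroni at 0.0125 covers each pair, and 0.025 covers each single visit.
3. **Otherwise**, label the time-point results descriptive and make no confirmatory claim at individual visits.

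Cost of the fixed order, for 125 per group: none at T2. At T4, up to about 2.6 points of power without baseline adjustment and 0.4 with it in the fading scenario, and up to about 5.6 and 0.6 in the constant scenario. Later visits cannot be claimed if T2 fails.

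Cost of the step-down rule: in the planned scenarios, at most about 3.5 points without baseline adjustment (fading: gated power 86/78/64% becomes 85/75/63%) and about 0.2 with it. Other patterns cost more. With effects 7.5, 6.375, 0, the 8-month power falls from 83% to 76% unadjusted, or from 99.4% to 98.8% adjusted. With an assumed steep fade of 7.5, 3, 0, it falls by about 10 points at 8 months even with adjustment.

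Either rule needs only a sentence or two of text and no change to design or data collection.

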7.4 Data Management/Audit

7.4.1 Data management.

- A. Rapid Case Ascertainment (RCA) will maintain the patient referral database for the proposed research project on a secure network drive at the NC Central Cancer Registry. Downloaded files from the RCA project database to the researcher portal are encrypted with PGP software by RCA staff. The encrypted files are electronically transferred through SFTP to the secure integrated research system on the UNC server. The encrypted files on the UNC server is electronically retrieved through SFTP by the authorized personnel who directly works on the research project, including the project coordinator and the health educator.
- B. All survey data will be collected and managed by research staff using REDCap. study ID numbers will indicate the identities of subjects, and this information will be

accessible only to the study investigators. All questionnaires will bear study ID numbers only. Research team staff will conduct all telephone survey sessions in a private workstation in a private office designated to the research team. The telephone surveys will be recorded and reviewed by the PI, research staff at the project office to ensure adherence to the study protocol as well as data completeness and accuracy. We will randomly check at least 10% of the recordings against completed data for adherence to protocol, data completeness, and accuracy.

REDCap online database will be managed by the TraCS Clinical Research Data Management Service. NC TraCS is a key initiative of the Biomedical Informatics core of the UNC-Chapel Hill CTSA. The purpose is to provide a system and associated support resources, to enable efficient and high-quality collection and management of research data that is standards-based in design, development and implementation. Standard features of electronic clinical research data management systems are available in the web-based systems provided with the service. These include interactive data entry with real-time field validation, lab data imports, audit logs to record database modifications, database integrity checks, security (in logins, permissions based on need, and encryption), reporting, forms inventory, and exports to common statistical packages for analysis. Logging tracks all data entered in REDCap so that it can be traced back to the person who entered it. No data can be changed without showing who has made the changes. This allows the study team to ensure there is security and integrity of the data collected and submitted, there are controls surrounding this aspect. REDCap also provides for principle investigator to sign off on the data, as required in FDA studies. Although users can modify data based on their permissions, they cannot delete the subject or history of that subject. Requests to delete a subject must be made to the REDCap system administrator. Our database system provides for secure web-based data entry with the data stored on servers that staff at NC TraCS maintain. The data is encrypted during transmission. The servers are located in a secure campus area with all the appropriate physical security measures in place. The web and database servers are monitored by the TraCS IT staff, patched frequently, and scanned by a third-party vendor to ensure that they are protected against known vulnerabilities. The scanning application is the standard service for the entire campus. Access is by individual user id and is restricted to the forms and/or functions that the user needs to have. The applications themselves are written using open source tools and have also been scanned by campus security office to ensure that the applications also are protected from known exploits. The data is backed up to electronic media on a daily basis. The electronic media is secured by ITS stored in a secure area separate from the servers.

- C. The study website for PERC and NCI landing is hosted and maintained by the Communication for Health Applications and Interventions (CHAI) of the UNC Lineberger Comprehensive Cancer Center. The web activity data of all participants will be deidentified (using randomly assigned user IDs) and automatically tracked via a built-in feature of the study website. The de-identified web activity data from the PERC website and the NCI website landing page at CHAI will be automatically electronically transferred through SFTP to the research office at the School of Nursing on a weekly basis.
- D. All administrative data (including randomization, referral data) will be centrally managed using REDCap at the PI's research office at the School of Nursing and accessed only to the study investigators and research staff. These administrative data

will be managed separately from the deidentified, password protected, encrypted and securely transferred data including surveys and web activity data. The PI and project coordinator will examine weekly the accuracy of the data files and completeness of the data.

7.4.2. Data Monitoring/Audit.

Per our consultation with the DSMB at UNC School of Medicine, although this is a randomized clinical trial, a DSMB is not needed because this study is of such low risk. With a primary outcome of change in quality of life (QOL) between the PERC intervention and the usual care plus NCI website control groups, there would not be anything significant to provide to the DSMB that might signal a reason for the DSMB to stop a study. However, we will implement a data and safety-monitoring plan to ensure the safety of participants as well as the validity and integrity of the data. The data monitoring plans are as follows:

A.Oversight for this study will be provided by the PI with input and advice from the team. An Adverse Event Monitoring Committee oversees the conduct of the study. Chaired by the [name] (PI), the committee will be comprised of all of the Co-investigators: Drs. [name], [name], [name], [name], [name], [name], and [name]. [name] will chair the committee, which will meet as needed to review the activities of the study including management, personnel, recruitment, performance, and any emerging problems.

The research staff will ensure all entry criteria are met prior to the initiation of the protocol and all study procedures and reporting of adverse events and unanticipated events will be performed according to the IRB-approved protocol. Any actions taken and associated follow-up activities will be recorded in the study database. All intervention-related adverse events will be reported by the PIs to the IRB within 3-7 days. The PI will submit necessary reports to NINR. The PI and the Adverse Event Monitoring Committee will assess the level of risk from adverse events as mild (no interference in usual activities); moderate (some interference in usual activities); or severe (usual activities were significantly interrupted). The PI and the Adverse Event Monitoring Committee will rate the assessment of attribution to the study as not related, unlikely, possible, probable, or definite.

B.An Independent monitor, [name] (UNC Urologist), will be independent from the present study design and implementation and will be available as needed to advise oversight committees

To protect the confidentiality of participant data, the research team will conduct all research activities related to data processing involving identifiable data in a private office at the University of North Carolina-Chapel Hill School of Nursing (UNC-CH SON) that is dedicated to the project. This study has minimum hardcopy research records; the PI and the Safety Officer will ensure all records to be saved in a locked cabinet in the locked private office. With most data and documents being electronic, the PI and the Safety Officer will ensure that the identifiable and de-identified data and documents are saved separately in different project folders in the password-protected and encrypted, shared drive at the UNC-CH SON, which is on a secure UNC server. Only authorized key study personnel will have access to the identifiable information.

The de-identified electronic data will include survey recordings and the recordings of monthly meetings between the educator and study participants for

quality control, survey data, study progress data and documents, and web activity tracking data. The PI and the Safety Officer will ensure that these data are tracked using study ID with no patient identifiable information attached. As a part of the UNC network and complying with UNC security regulations, the IT staff at SON works closely with the campus IT and other technology groups to ensure both security and efficiency for the proposed study.

Adverse event reports and annual summaries will not include participant-identifiable material. Each will include the identification code only.

